8. ANALYSIS POPULATIONS/ ANALYSIS SETS

The following patient populations will be used for the analyses as specified afterwards:

- All patients analysis set (ALL):** The ALL patient set includes all patients having been enrolled.
- Safety set (SAS):** The safety analysis set consists of data for all patients who were randomized and received at least one dose of trial medication.

3. **Full analysis set (FAS):** The full analysis set is defined as all patients of the SAS population with at least one measurement of the ADA titer at baseline (screening).
4. **Per Protocol set (PPS):** The PPS consists of all patients of the FAS for whom no relevant protocol deviations were documented.
5. **PK/PD set (PKS):** All patients in the SAS having at least one pre- and post-dose PK value at one visit.

The decision whether a protocol deviation is relevant or not for the exclusion of patients from the PPS set will be made case-by-case in a data review meeting before unblinding.

Assignment of analysis populations to analyses:

1. **ALL:** Presentation of information under sections study population (e.g. patient disposition, except termination/ withdrawal information).
2. **FAS:** Analysis of the primary endpoint, the key secondary endpoints and secondary endpoints referring to ADA response characterizations.
3. **SAS:** Safety parameters and analysis of study drug administration/ extent of exposure and termination/ withdrawal information.
4. **PKS:** Pharmacokinetic and pharmacodynamics endpoints

Main conclusions of the primary endpoint will be drawn from analyses based on the FAS. A secondary analysis of the primary endpoint will be based on the PPS.

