9. HANDLING OF DROP-OUTS OR MISSING DATA

In general no imputations will be made for missing values. Summaries will be based on observed data/ valid cases only.

There are some exceptions:

1. Any AE with missing relationship will be considered as possibly related to the study drug.
2. For flagging adverse events into pre-treatment/ treatment-emergent and medication into previous and concomitant, the following rules will be applied (the calculation of durations if foreseen won't use imputed data):

Date	Imputation rule
Partial/ Missing Start Date	
 • Missing day - Impute the 1st of the month unless year and month is same as year and month of first dose of study drug or date of screening in case study drug started earlier then impute first dose date • Missing day and month – impute 1st January unless year is the same as first dose date then impute first dose date • Completely missing – impute first dose date unless the end date suggests it could have started prior to this in which case impute the 1st January of the same year as the end date
Partial/ Missing End Date	
 • Missing day - Impute the last day of the month unless year and month is same as year and month of last dose of study drug then impute last dose date • Missing day and month – impute 31st December unless year is the same as last dose date then impute last dose date • Completely missing – impute date of last dose • If imputed end date < imputed start date, take the imputed start date to impute the end date

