16. METHODS OF PHARMACOKINETIC (PK) AND PHARAMCODYNAMIC (PD) ENDPOINT ANALYSIS

Pharmacokinetic and pharmacodynamic analyses will use the PKs population.

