16.1 PK and PD parameters

The pharmacokinetic metrics as listed below will be obtained from individual plasma concentration-time data by non-compartmental analysis using the computer programs WinNonLin® Version 5.4 or SAS Version 9.4.

The following PK parameters will be calculated for dasiglucagon and GlucaGen® analytes from the individual plasma concentration versus time profiles after each active treatment per visit.

Symbol	Definition	Calculation
C_{\max}	Measured maximum serum concentration after administration	Taken directly from analytical data, selected from individual concentration data
t_{\max}	Sampling time until reaching C_{\max}	Taken directly from analytical data, selected from individual concentration data
$AUC_{0-30\text{min}}$	Area under the concentration-time curve from zero up to the concentration at 30min	Linear trapezoidal rule for the ascending part of the concentration-time curve, logarithmic trapezoidal rule for the descending part.
$AUC_{0-90\text{min}}$	Area under the concentration-time curve from zero up to the concentration at 90min	Linear trapezoidal rule for the ascending part of the concentration-time curve, logarithmic trapezoidal rule for the descending part.

Table 2: Pharmacokinetic metrics

The following PD measures for glucose will be calculated from the plasma results for each treatment group and visit:

Symbol	Definition	Calculation
CE_{\max}	Change from baseline plasma glucose to maximum plasma glucose measured post-dose	Taken directly from analytical data, selected from individual concentration data
t_{\max}	Time to maximum change from baseline CE_{\max}	Taken directly from analytical data, selected from individual concentration data
$AUE_{0-30\text{min}}$	Area under the baseline-adjusted effect curve from zero up to the concentration measured at 30min	Linear trapezoidal rule for the ascending part of the effect-time curve, logarithmic trapezoidal rule for the descending part.
$AUE_{0-90\text{min}}$	Area under the baseline-adjusted effect curve from zero up to the concentration measured at 90min	Linear trapezoidal rule for the ascending part of the effect-time curve, logarithmic trapezoidal rule for the descending part.

Symbol	Definition	Calculation
Inc20 _{0-30min}	Increase of ≥ 20 mg/dL within 30 minutes after treatment	Binary variable derived from raw glucose concentration measured at 30min after dosing. In case glucose has reached at least 20 mg/dL the parameter is set to 'yes', otherwise to 'no'

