3.1 Definition of analysis populations

The Study Protocol and the Statistical Analysis Plan (v0.2) detail the following analysis sets:

1. **All patients analysis set (ALL)** includes all patients that have been enrolled.
2. **Safety set (SAS) includes** all patients who were randomized and received at least one dose of trial medication.
3. **Full analysis set (FAS)** is defined as all patients included in the SAS population with at least one ADA measurement at baseline (Visit 2).
4. **Per Protocol set (PPS)** consists of all patients included in the FAS for whom no relevant protocol deviations were documented
5. **PKPD set (PKS)** is defined as all patients included in the SAS with at least one pre- and post-dose PK/PD value at one visit (Visit 2/4).

Assignment of analysis populations to analyses:

The study population including information on subject disposition and protocol deviations will be presented based on the ALL analysis set.

Analysis of primary endpoint, key secondary endpoints and secondary endpoints referring to ADA response characterizations will be made for the FAS analysis set.

A secondary analysis of the primary endpoint will be based on the PPS.

The SAS set will be used to analysis safety parameters and study drug administration/extent of exposure.

The PKS set will be used for the analysis of pharmacokinetic and pharmacodynamics endpoints.

Adherence to the study protocol is defined based on defined protocol deviation categories. The decision whether a subject adhered to the protocol was made by classifying reported and/or derived deviations into major and minor protocol deviations.

Major protocol deviations led to exclusion from the PP set.

The decision whether a protocol deviation is major or minor was done at the Blind Data Review Meeting.

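### The glucose endpoints are analysed in a set defined by PK values, and the Inc20 row of Table 3 neither codes the stated endpoint nor says how a missing 30-minute glucose is handled

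*SAP*

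**What the plan says.** **Analysis set.** SAP section 8, item 5, names a PK/PD set (PKS) but defines it by drug concentrations only: "All patients in the SAS having at least one pre- and post-dose PK value at one visit". The same section assigns both PK and PD endpoints to it. Section 16 repeats this ("Pharmacokinetic and pharmacodynamic analyses will use the PKs population"), and every PD table and figure listed in Appendix C carries the PKS label. No SAP text makes glucose a condition of entry.

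The Data Review Meeting Protocol included with the SAP cites the study protocol and SAP v0.2 as its sources. Its section 3.1 nevertheless gives another rule: SAS patients "with at least one pre- and post-dose PK/PD value at one visit (Visit 2/4". Protocol section 10.1.2 defines only the safety, full and per-protocol sets, so it does not settle the matter.

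**Inc20.** SAP section 15 lists as a PD endpoint a plasma glucose rise of at least 20 mg/dL within 30 minutes of treatment. Table 3 in section 16.1 derives it as follows: "Binary variable derived from raw glucose concentration measured at 30min after dosing", then "In case glucose has reached at least 20 mg/dL the parameter is set to 'yes', otherwise to 'no". There is no third category.

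**Missing values.** SAP section 9 states: "In general no imputations will be made for missing values". It bases summaries on observed cases and lists exceptions (AE relationship, and AE and medication dates) that do not include Inc20. Section 16.2 leaves missing post-dose values unreplaced. Section 6 removes missing values from percentage denominators.

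**The concern.** Drug concentration and glucose are separate measurements. Exposure is assayed at specialty laboratories (Protocol 7.2 and 7.4.6) and glucose at the clinical laboratory (Protocol 7.6.3). One can fail while the other is complete, so glucose results should not depend on whether the PK assay succeeded. Two wordings of the same set also leave it unclear which one governed when patients were classified.

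Inc20 was added by Amendment 2 to support bridging to the pivotal efficacy trial. According to Protocol 5.1, every phase 2 patient met the corresponding criterion. Near 100%, the result depends on exactly what counts as 'yes', 'no' and missing, and on these points the Table 3 row is wrong or silent.

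**Working it through.** The plan gives no design figure for Inc20. Its only sample-size figure, 45 completers per arm, concerns ADA incidence. It reproduces (ln 0.10 / ln 0.95 = 44.89, rounded up to 45) and has no bearing here.

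**1. Who the PKS leaves out.** PK and glucose are both drawn pre-dose and at 5, 10, 30, 60 and 90 minutes at Visits 2 and 4 (SAP 15). Entry needs one pre-dose and one post-dose PK value at one visit. A patient sampled at both visits is excluded only if each visit fails, meaning no pre-dose value or all five post-dose values absent. A patient sampled at Visit 2 only is excluded if Visit 2 alone fails in that way.

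**2. How the definitions differ.** The term PK/PD in the review document can mean either or both.

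| Patient has, at one visit | SAP 8 | Review document, PK or PD | Review document, PK and PD |
|---|---|---|---|
| PK pair and glucose pair | in | in | in |
| Glucose pair only | out | in | out |
| PK pair only | in | in | out |

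The three readings agree only in the first row.

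**3. What exclusion does to the Inc20 rate.** Assume 112 / 2 = 56 treated per arm, all responders. Dropping k patients leaves the rate at 100%. The exact 95% lower limit, 0.025^(1/n), moves from 93.6% (n = 56) to 93.0% (n = 51, k = 5). The effect is small. The limits are illustrative, because SAP 16.3 and 16.4 plan no interval for PD results.

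**4. A missing 30-minute glucose.** PKS entry at one visit carries the patient into both visits, while PD metrics are computed per visit. A patient with a Visit 2 PK pair and no Visit 4 sample is therefore in the set with no Visit 4 glucose. The plan expects 112 − 90 = 22 non-completers, about 11 per arm; how many leave before Visit 4 is not stated. Missed PK/PD samples are foreseen and graded minor (Data Review Meeting Protocol 3.3, item 5.1).

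With 56 per arm and every observed patient responding:

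| Missing values | 'Otherwise no' taken literally | Observed cases (SAP 6, 9, 16.2) |
|---|---|---|
| 1 | 55/56 = 98.2% | 55/55 = 100% |
| 2 | 54/56 = 96.4% | 54/54 = 100% |
| 3 | 53/56 = 94.6% | 53/53 = 100% |
| 5 | 51/56 = 91.1% | 51/51 = 100% |

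The literal reading costs 1/56 = 1.8 points per missing value. The general rules cost nothing.

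**5. Raw level against rise.** The pre-dose target is 70–150 mg/dL.

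| Pre-dose | Level the endpoint needs | Level Table 3 needs | Result if glucose does not change |
|---|---|---|---|
| 70 | 70 + 20 = 90 | 20 | Table 3 'yes'; endpoint not met (rise 0) |
| 150 | 150 + 20 = 170 | 20 | Table 3 'yes'; endpoint not met (rise 0) |

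Starting at 70, a patient would have to fall by more than 50 mg/dL to be scored 'no'. Table 3 also uses only the 30-minute sample, whereas the endpoint covers any time within 30 minutes and so includes the 5- and 10-minute samples.

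**The case against.** **On the set.** The SAP calls it a PK/PD set, and the document used to classify patients says PK/PD value. If that means either, a glucose-only patient qualifies and nobody is lost. The review document's contents also list a section 3.2 on exclusions unrelated to protocol deviations. Its text was not available for this review and may have settled the rule. This limits any claim about what was done. It does not remove the conflict, because the SAP text is explicit about PK and the review text is ambiguous.

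A reader might infer that one lost PK sample removes a complete glucose profile, or that each dropped patient visibly shifts the response rate. Steps 1 and 3 show otherwise. A missed draw would also often remove both samples, since they share nominal times.

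**On missing values.** A reader might infer from "the parameter is set to 'yes', otherwise to 'no" that an absent 30-minute sample is scored as a treatment failure. The documents do not say so. Table 3 speaks of a measured concentration, and SAP sections 6, 9 and 16.2 together point to a missing Inc20. What stands is narrower: the specific derivation row has two outcomes and no reference to those rules, so a programmer could apply it literally.

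**On the raw level.** The Definition column of the same row does say increase, so the intention is recoverable. The Calculation column, which would be programmed, still contradicts it.

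**Conclusion.** Three things hold.

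- The SAP analyses glucose in a set defined by PK, and the review document defines that set differently. The number affected is probably small but is not given.
- The Table 3 calculation for Inc20 does not measure the stated endpoint. As written, practically every patient with a 30-minute sample would be 'yes', so the main error in the row favours success.
- The treatment of a missing 30-minute value is left to inference. The better reading is missing, not failure. If the literal reading were programmed, the cost would be about 1.8 points per missing value, assuming 56 per arm and full response among those observed.

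The primary ADA analysis is unaffected. The set conflict and the missing-value gap are minor. The raw-level coding needs correcting before Inc20 can serve the bridging purpose for which it was added.

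**What to change.** - **PD set.** Define it per visit: SAS patients with a pre-dose and at least one post-dose glucose at that visit, regardless of PK. Keep the PKS for PK endpoints only. Use identical text in the SAP and the data review document.
- **Inc20.** Score 'yes' if post-dose minus pre-dose glucose is at least 20 mg/dL at any sample up to and including 30 minutes, and 'no' otherwise, among patients with both a pre-dose and a 30-minute glucose at that visit. Set it to missing for everyone else. Requiring the 30-minute sample matters: if earlier samples alone could qualify a patient, those without a 30-minute value could enter only as successes.
- **Pre-dose glucose.** State that the SAP 16.2 rule setting all pre-dose concentrations to zero for the PK/PD metrics does not apply to glucose. Otherwise the difference reduces to the raw level again.
- **Reporting.** Give the number missing per arm and visit, with a sensitivity count that scores missing as 'no'.

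The cost is SAP and data-review wording and a short programming change. No new data are needed.

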9. HANDLING OF DROP-OUTS OR MISSING DATA

In general no imputations will be made for missing values. Summaries will be based on observed data/ valid cases only.

There are some exceptions:

1. Any AE with missing relationship will be considered as possibly related to the study drug.
2. For flagging adverse events into pre-treatment/ treatment-emergent and medication into previous and concomitant, the following rules will be applied (the calculation of durations if foreseen won't use imputed data):

Date	Imputation rule
Partial/ Missing Start Date	
 • Missing day - Impute the 1st of the month unless year and month is same as year and month of first dose of study drug or date of screening in case study drug started earlier then impute first dose date • Missing day and month – impute 1st January unless year is the same as first dose date then impute first dose date • Completely missing – impute first dose date unless the end date suggests it could have started prior to this in which case impute the 1st January of the same year as the end date
Partial/ Missing End Date	
 • Missing day - Impute the last day of the month unless year and month is same as year and month of last dose of study drug then impute last dose date • Missing day and month – impute 31st December unless year is the same as last dose date then impute last dose date • Completely missing – impute date of last dose • If imputed end date < imputed start date, take the imputed start date to impute the end date

10. STUDY POPULATION

Tables in this section will be provided for the SAS/ALL populations.

10.1 Patient numbers in each country and investigational site

Patient numbers/ percentages in each country and patient numbers/percentages in each country and site will be presented by treatment group.

10.2 Patient disposition

Patient disposition information will be summarized for all patients by treatment group. The patient disposition summary will include:

- the number of enrolled (=signed informed consent) patients,
- the number of re-screened patients,
- the number of screening failures (as determined by the screening failure question at screening or in case of not fulfilling eligibility criteria at visit 2/ day 0),
- the number of randomized patients,
- the number of patients in the analysis set SAS
- the number of patients in the analysis set FAS
- the number of patients in the analysis set PPS
- the number of patients in the pharmacokinetic/ pharmacodynamic analysis set
- the number of patients with previous exogenic glucagon exposure
- number of patients having a regular follow-up (yes/no)
- the number of patients, who completed the study (V7)

Patient numbers/ percentages in each of the sets mentioned above will be displayed by treatment group.

10.3 In- and exclusion criteria, eligibility criteria

Details on in- and exclusion criteria not met at screening, and on re-check of in- and exclusion criteria (re-screening) and visit 2/ day 0 questions on eligibility, will be listed and not tabulated.

Check questions at dosing day referring to possible exclusion criteria (filled in at screening, visit 2/ day 0 and possible re-scheduled visits as well as unscheduled dosing visits (for ADA positive patients)) will be listed.

10.4 Trial termination form and withdrawal criteria information

Trial termination form

The number of patients who completed/ or discontinued the study will be tabulated by treatment regimen with counts and percentages for all patients. In addition, for patients who discontinued, the primary reason will be tabulated by treatment group. Number/ percentage of patients, whose treatment were unblinded or not, will be displayed as well.

Withdrawal criteria information

Patient withdrawal criteria at all regular visits and further unscheduled visits (e.g. including ADA unscheduled visits) are not mapped into SDTM domains. Therefore no data will be displayed.

10.5 Demographic and baseline characteristics

10.5.1 Demographics

A table for the demographic data will be prepared with summary statistics for age at signing the IC (years) (both as continuous and as categorized age class variable), gender, race and ethnicity. The demographics table will be generated for all patients by treatment group.

10.5.2 Informed consent

Information concerning informed consent will be listed.

10.5.3 Medical history

Medical history will be displayed for the ALL and the SAS population.

Indication specific medical history (diabetes history)

Time since detection of diabetes 1 (based on date of informed consent and start date of diabetes 1) (years) will be tabulated with descriptive statistics by treatment group. If the day is not available, the calculation of duration will be based on month and year only, setting the start day to 1. In case only the year is available, the start day will be 1 and the start month will be January.

General medical history/ surgical history including concomitant diseases

All entries in this section will be coded using MedDRA, current version 20.0 or higher. Frequency tables will be prepared by treatment group stratified by MedDRA terms (SOC,

PT) showing the number of entries in each SOC and PT and numbers/ percentages of patients being affected.

10.5.4 History of alcohol or drug abuse

Number/ percentage of patients having a history of alcohol or drug abuse will be displayed by treatment group. Results of alcohol breath test at screening and urine drug screen test will be included in the same tabulation. Results of further alcohol breath tests and urine drug screen tests can be found in the patient withdrawal criteria (see sec. 10.4) and the dosing day exclusion criteria (see sec. 10.3).

10.5.5 Other information documented at screening

Analyses of other screening or baseline variables, which are documented at screening/ baseline and/ or have further evaluations after the screening/ baseline visit will be described in the following sections:

- Physical examination: see sec. 14.3.2
- Vital signs, see sec. 14.3.1
- 12-lead electrocardiogram (12-lead ECG), see sec. 14.4
- Central safety laboratory (hematology, biochemistry, coagulation, urinalysis, urine drug screening, urine pregnancy test), see sec. 14.2
- Previous medication, see sec. 14.5
- Adverse events, see sec. 14.1

11. PRIMARY IMMUNOGENICITY AND SECONDARY IMMUNOGENICITY ENDPOINT ANALYSES

11.1 Primary immunogenicity endpoint

The primary endpoint is the evaluation of immunogenicity of repeated single doses of dasiglucagon and GlucaGen® and comprises:

Overall ADA incidence

Overall ADA incidence is defined as the percentage of the combined results of treatment-induced ADA-positive patients and treatment-boosted ADA-positive patients (as defined in the secondary endpoints section) and the total number of evaluable patients, excluding baseline-positive patients without any samples available after drug administration.

11.2 Secondary endpoints

Secondary endpoints consider key secondary endpoints and secondary endpoints as listed below:

A) Key secondary endpoints

- **Treatment-induced ADA incidence**
Treatment-induced ADA incidence is calculated as the percentage of the total number of evaluable patients that were ADA negative at baseline and ADA positive after drug administration relative to the total number of evaluable patients, excluding baseline positive patients without any samples available after drug administration.
- **Treatment-boosted ADA incidence**
Treatment-boosted ADA incidence is calculated as the percentage of baseline ADA-positive patients with significant increases (≥ 5 -fold) in ADA titer after drug administration relative to the total number of evaluable patients, excluding baseline-positive patients without any samples available after drug administration.

B) Secondary endpoints

- Incidence and titer of neutralizing activity of ADA positive patients
- Incidence of cross-reactivity of ADA positive patients towards endogenous glucagon
- Kinetics of ADA: The timing and duration of detected ADA response

